More than 64,000 Americans died from drug overdose in 2016 and drug overdose is now the most common cause of death for people under 50 years old in the United States (1). Furthermore, the number of overdose deaths is increasing with the rise of abuse of powerful synthetic opioids, such as fentanyl. In May of 2017, the National Institutes of Health (NIH) and National Institute on Drug Abuse (NIDA) directors Drs. Collins and Volkow (3) outlined how research may help reduce the death toll associated with the current opioid epidemic; one of the current critical needs is the development of new overdose-reversal interventions, including wearable technologies that can detect an (impending) overdose from physiological signals to signal for help, or trigger a coupled automated injection of naloxone. Automated detection of overdose is essential because most opioid overdoses occur when individuals are alone and unobserved by family members or first responders. Opioids cause respiration to slow and become irregular due to mu-opioid receptor mediated suppression of respiratory related regions of the brainstem and spinal cord. Importantly, there are characteristic early changes in breathing patterns that indicate a progression towards significant hypoventilation, but there is currently no method to measure these patterns non-invasively without large hospital equipment. Recently, there has been a renewed interest in respiratory monitoring using tracheal sounds (2, 4, 5). Tracheal sounds originate from the vibrations of the tracheal wall and surrounding soft tissues caused by gas pressure fluctuations in the trachea. These sounds can be collected from a microphone or a piezo-electric film transducer placed over the trachea and have been processed to monitor respiratory rate and to estimate respiratory flow. We hypothesize that individual trends in tracheal sounds detected by a machine-learning algorithm will provide an early warning sign of the onset of hypoventilation as a result of opioid overdose in humans. The aim of this study is to develop a machine-learning algorithm that detects impending hypoventilation as a result of opioid overdose from tracheal sound. This algorithm could eventually be integrated with a miniature tracheal sound sensor and could be used to detect impending respiratory depression in the outpatient setting as well as in the hospital.

A. Specific Aims

We hypothesize that advanced analysis of tracheal sound can be used to predict hypoventilation due to opioid overdose.

The specific aim of this proof of concept study is to collect tracheal sound data in 20 healthy subjects undergoing an incremental infusion of fentanyl to induce mild to moderate hypoventilation (also called permissive hypercapnia). Study subjects will receive supplemental oxygen to prevent hypoxemia. The tracheal sound data will be refined using advanced signal processing techniques and machine learning to assess whether it is possible to detect and predict the onset of hypoventilation.

The long-term objective of this project is to develop a real-time monitoring system based on tracheal sound that can be used to detect changes in minute ventilation and alarm before significant hypoventilation occurs due to an overdose of anesthetics and/or analgesics.

B. Background and Significance

RTM Vital Signs, LLC is collaborating with Thomas Jefferson University to develop a non-invasive Tracheal Sound Sensor that continuously monitors and analyzes sounds from the trachea to determine upper airway patency and the adequacy of an ambulatory person's respiratory rate (RR) and tidal volume (TV) to maintain a sufficient minute ventilation (RR X TV).

Over the last decades various mathematical methods have been developed to estimate respiratory rate and respiratory flow from tracheal sounds (2). Airflow sounds are known to occur at a frequency of 200-2000 Hz while snoring sounds occur in the 0-200 Hz band (2). There is a near-linear relationship between airflow in the trachea and respiratory sounds - increasing flow increases the amplitude of sounds. Additionally, different transformations can be applied continuously on recorded tracheal sound to extract specific information.

Previous studies have looked at the average power, envelop, spectral power, and entropy of sound signals. One of the most robust models to estimate respiratory flow from tracheal sound uses the entropy of tracheal sounds (a measure

[figure not shown]

Figure 1. Actual tracheal airflow (solid line) measured with a reference pneumotachometer and estimated airflow using a microphone over the sternal notch and entropy model (dashed line). Figure modified from Yadollahi and Moussavi (2).

of sound complexity) to determine tracheal airflow during inhalation and exhalation (Figure 1) (2, 4).

A pilot human clinical study that utilizes fentanyl to induce mild and moderate hypoventilation will be conducted in 20 healthy adults to collect the data necessary to develop a diagnostic algorithm that functions as a risk-index score that continuously predicts the onset of mild and moderate hypoventilation using signal processing and machine learning methods.

Informed Consent/Screen- Visit # 1:

Subjects will arrive at the Department of Anesthesiology's research office. [name] will review the informed consent document and the inclusion/exclusion criteria. Subjects will complete a Drug Abuse Screening Test (DAST)(6) to determine their risk for substance abuse (Attachment 1). They will also provide a urine sample to perform a drug screen toxicology analysis. For women, we will also provide urine pregnancy testing. [name] will also review the informed consent document, answer any of the subject's questions and obtain a signed consent form. Each subject will receive a copy of the consent form. [name] will then perform a detailed history and physical exam and review the subject's vital sign data. [name] will then schedule the clinical study visit # 2.

Human Clinical Study - Visit # 2:

Study subjects will be instructed to refrain from eating after 11 pm (NPO) the day prior to the study and to arrive at Thomas Jefferson University Hospital around 7 am on the morning of study visit # 2. A urine drug screen toxicology test will be repeated on all study subjects. For female subjects, we will also conduct urine pregnancy testing.

Subjects will be studied in a hospital clinical environment containing an anesthesia machine, vital sign monitors and routine emergency equipment, medications and supplies. All study subjects will be managed by [name], D.O. an experienced board-certified anesthesiologist with extensive experience in the respiratory effects of an IV infusion of fentanyl. Subjects will be continuously monitored using standard anesthesia vital sign monitors (ECG/upper arm cuff BP/pulse oximeter, Datex Ohmeda) and a BIS sedation monitor (Covidien) according to American Society of Anesthesiology standards. A contact microphone (BIOPAC TSD108) will be adhered to the skin over the trachea (above the sternal notch) with double-sided tape and a Tegaderm bandage. An accelerometer will be adhered to the skin close to the microphone.

A catheter will be inserted into a radial artery using ultrasound guidance, lidocaine local anesthetic and aseptic technique to acquire samples for blood gas analysis and continuously monitor the arterial blood pressure (Edwards Lifesciences Truwave). A catheter will also be inserted into a peripheral vein using aseptic technique to facilitate the infusion of fentanyl. Oxygen will be continuously delivered using a soft tight-fitting face mask connected to an anesthesia circuit (FIO2-1.0) with a side-port for continuous sampling of inspired/expired gas (sampling line to BIOPAC CO2100C gas analyzer). Respiratory rate and airflow will be continuously measured using a commercial reference pneumotachometer attached to the inlet of the face mask (BIOPAC TSD117A). All cardiovascular, respiratory, and sound monitoring will be continuously recorded through a BIOPAC MP150 data acquisition system connected to a desktop computer. Pictures may be taken after instrumentation.

Monitored study subjects will be instructed to rest comfortably in the supine position and refrain from talking. A standard IV dose of Ondansetron will be administered to minimize the risk for nausea/emesis. A standard IV dose of glycopyrrolate may be administered to minimize the risk for bradycardia. Vital signs and respiratory data will be recorded

during a 1-hour baseline period while sampling arterial blood every 15 minutes to measure pH, PaCO₂, PaO₂, HCO₃, SaO₂ and lactate concentrations (Epoc blood analysis system, Siemens, München, Germany).

After an initial bolus of 1.0 mcg/kg, a stepwise continuous intravenous infusion of fentanyl will be started at time zero (Figure 2). The infusion will start at 1.5 mcg/kg/hr and will be increased by 1.5 mcg/kg every 30 minutes. The infusion will be continued for a maximum duration of 3 hours (final infusion rate 9.0 mcg/kg/h). In a 30-year old 70 kg man, the proposed stepped infusion is projected to cause a gradual increase in fentanyl plasma concentration up to a maximum concentration of 5.8 ng/mL (Figure 3). Respiratory depression typically occurs anywhere in the 2.0 – 6.0 ng/mL fentanyl plasma concentration range (7, 8) while loss of consciousness occurs around 34 ± 7 ng/mL (7).

Vital sign monitor data, CO₂ waveform data, reference pneumotach data, and tracheal sound data will be continuously recorded throughout the infusion protocol. Arterial blood gases will be measured every 10 minutes, or immediately after the decision is made to stop the infusion protocol. The fentanyl infusion will be discontinued prior to the end of the 3 hour protocol if: (1) the PaCO₂ exceeds 60 mm Hg in two consecutive blood gas measurements (primary end-point), (2) the subject requires positive pressure bag/mask assisted ventilation by the anesthesiologist, or (3) the SaO₂ falls below 90% on supplemental oxygen (FIO₂=1.0).

The primary endpoint of the study will be the onset of moderate hypoventilation, defined as two consecutive arterial PaCO₂ measurement ≥ 60 mmHg. This level of opioid induced hypoventilation is clinically significant because based upon the alveolar gas equation and the Henderson-Hasselbalch equation- breathing room air (FIO₂ 21%) at sea level (barometric pressure 760 mm Hg) (9), a PaCO₂ of 60 mm Hg will decrease the PaO₂ from 159 mm Hg to 75 mm Hg to produce an arterial partial pressure of oxygen (PaO₂) ~75 mmHg. The respiratory acidosis will cause the hemoglobin oxygen dissociation curve to shift to the right and downward leading to an arterial hemoglobin oxygen saturation of ~88% SaO₂.

Respiratory and vital sign data will continue to be collected for another 2 hours after discontinuation of the fentanyl infusion. Arterial blood will be sampled every 15 minutes for pH and blood gas analysis. The total volume of blood sampled will be approximately ~45 ml over a 6 hour study period (25 samples x 1.5 ml/sample = 45 ml). The narcotic antagonist Naloxone and other emergency medications will be immediately available as needed to ensure safety. After the 2 hour post infusion measurements, subjects will eat a meal and be observed for another hour or more to confirm adequate minute ventilation.

After completion of the experiment, study subjects will be given oral and written instructions similar to patients undergoing an outpatient surgical center procedure under general anesthesia. Each subject will receive a phone call around 9 pm that evening and a phone call 5-7 days later to confirm no study related adverse events.

Summary of Subject Monitoring:

- 1) Radial artery catheter to monitor and record the arterial blood pressure waveform.
- 2) Heart rate & rhythm will be monitored and recorded by an electrocardiogram.
- 3) Respiratory flow and tidal volume will be monitored and recorded using a pneumotach.
- 4) End-tidal CO₂ concentration and waveform will be monitored and recorded.
- 5) Hemoglobin oxygen saturation (SaO₂) will be measured and recorded.
- 6) Skin temperature will be measured and recorded.
- 7) Tracheal sounds will be measured and recorded using a microphone.
- 8) Body movement will be measured and recorded using an accelerometer.
- 9) Serial measurements of arterial blood pH, PaO₂, PaCO₂, bicarbonate, and lactate concentration.
- 10) Serial measurement of the Bispectral Index (BIS).

Anticipated Problems and Alternative Approaches:

The anesthesiologist has the clinical experience to produce mild and moderate hypoventilation safely using an IV infusion of fentanyl. The research team does not anticipate any major difficulties in executing this protocol. The slow intravenous fentanyl infusion will reliably induce alveolar hypoventilation in a dose dependent manner. A similar method has been safely used by research anesthesiologists in multiple clinical studies (4, 8, 10). The degree of sedation and hypoventilation is mild to moderate and the risk of hypoxemia is minimal due to the use of supplemental oxygen by face mask, continuous pulse oximetry, and frequent PaO₂ measurements. [name] is a board-certified Anesthesiologist with 35 years of expertise at TJUH managing patients with intravenous infusions of fentanyl and other anesthetics/medications that suppress minute ventilation. [name] will closely observe and clinically manage all of the study subjects until they are awake, alert and stable.

Figure 2. Fentanyl Infusion Protocol.

[figure not shown]
[figure not shown]

Figure 3. Projected plasma concentrations of fentanyl with the proposed stepped fentanyl infusion protocol. Using the European Society for Intravenous Anesthesia simulator (Tivatrainer, 11) we simulated the plasma concentrations of fentanyl that would be achieved with the proposed stepped fentanyl infusion protocol in a 30 year old man (70 kg, 170 cm). The specific kinetic model for fentanyl that is used by Tivatrainer has been published previously (10). The red line depicts the projected plasma concentration while the green line depicts the effect site concentration (both measured on left Y-axis, time in minutes on X-axis). The stepwise fentanyl infusion is depicted in boxes (infusion rate of 0.05 mg/mL fentanyl on right Y-axis, time in minutes on X-axis).

E. Statistical Methods

This is a pilot study and we therefore do not have prior data to conduct a power analysis. Because sound and physiological data will be collected continuously, even a relatively small number of subjects will provide a significant data set for algorithm development. If we assume a respiratory rate of 12 breaths per minute then: 12 breaths per min x 60 mins per hr = 720 breaths per hr; 720 breaths x 6 hr study time per patient = 4,320 breaths per patient; 4,320 breaths per patient x 6 subjects = 25,920 breaths for all 6 subjects. Previous studies on analysis of tracheal sound to track ventilation have used a similar n, with sometimes shorter protocols (2).

The performance of the developed prediction algorithm will be evaluated by looking at the mean absolute error in predicted PaCO₂ vs. the actual PaCO₂ and by comparing predicted time to hypoventilation during the fentanyl ramp vs. the observed time to hypoventilation. We plan to perform analysis on data from an initial 6 study subjects, then study up to 20 subjects to produce a more robust machine learning algorithm that detects/predicts the onset of mild and moderate hypoventilation.

F. Gender/Minority/Pediatric Inclusion for Research

Minorities will be eligible to participate in the research. Children (age < 18 years) will be excluded from participation. We aim to recruit robustly healthy young subjects for this initial proof of concept effort, because we anticipate that they will tolerate this protocol very well. We anticipate studying populations that are more varied if the proposed proof of concept study is successful.

G. Human Subjects

Inclusion criteria will be:

1. Healthy women/men between 18 and 40 years of age.
2. Negative history of drug or alcohol abuse.
3. Negative history of cigarette smoking in previous 6 months.
4. Negative history of active cardiac, vascular, pulmonary, renal, hepatic, nervous, metabolic or immune disease.
5. BMI < 30

Exclusion criteria will be:

1. Age < 18 years and > 40 years.
2. Pregnant or planning to become pregnant.
3. Positive history drug or alcohol abuse.
4. Positive drug screen for opioids, benzodiazepines, hypnotics.
5. Positive Drug Abuse Screening Test result (score of 6 or greater).
6. BMI > 30
7. History of sleep apnea.
8. History of cigarette smoking in previous 6 months.
9. History of difficult airway during anesthesia management.
10. History of allergy or skin sensitivity to tape, silicone, fentanyl, chlorhexidine.

Study Subject Recruitment & consent:

Twenty healthy volunteers will be recruited from the general population around Thomas Jefferson University using an advertising flier (Attachment 2). Potential subjects will contact the Anesthesiology

research nurse coordinator [name], R.N. to review the inclusion/exclusion criteria and schedule visit # 1 (Attachment 3, phone script). Subjects will arrive at the Department of Anesthesiology's research office. [name] will review the informed consent document and the inclusion/exclusion criteria. Subjects will complete a Drug Abuse Screening Test (DAST) (6) to determine their risk for substance abuse (Attachment 1). They will also provide a urine sample to perform a drug toxicology analysis. In female potential subjects, we will also perform a urine pregnancy test. [name] will also review the informed consent document with subjects during visit #1, answer any of the subject's questions and obtain a signed and witnessed consent form. Each subject will receive a copy of the consent form. [name] will then perform a detailed history and physical exam and review the subject's vital sign data. [name] will then schedule the clinical study visit # 2 in 2 to 6 weeks.

General Approach to Minimize Risk:

We plan to study only young and healthy subjects with a good airway, at very low risk for an anesthetic complication. Clinical trials have demonstrated the safety of managing hospitalized patients with mild to moderate permissive hypercapnia, as long as hypoxemia is avoided (12). Subjects will be studied in a hospital clinical environment containing an anesthesia machine, vital sign monitors and routine emergency equipment, medication and supplies. [name] will use TJUH standard of care operating procedures and other well-accepted safety strategies to minimize risk. Supplemental oxygen will be continuously delivered via face mask to significantly minimize the risk of hypoxemia during fentanyl induced hypoventilation.

We will use estimated maximum plasma concentrations of fentanyl up to 5.8 ng/mL. Studies on the respiratory depressive effect of fentanyl using similar incremental concentrations of fentanyl have been safely conducted (8, 10). Respiratory depression typically occurs anywhere in the 1.0 – 6.0 ng/mL (7) plasma concentration range while loss of consciousness does not occur until 34 ± 7 ng/ml (7). If respiratory depression needs to be reversed during the study, it can be rapidly reversed using one or more doses of IV naloxone.

Specific Procedures and Risks:

1. Radial artery catheterization: The radial artery will be catheterized using aseptic techniques after local anesthesia. A 5-cm 20-gauge catheter will be inserted using ultrasound guidance to minimize the potential need for multiple sticks, bleeding or hematoma. The anesthesiologist [name] has vast experience placing catheters in a radial artery. Rare risks associated with radial artery catheter insertion and use are thrombus formation, hand ischemia, and infection. These complications are rare in healthy subjects without vascular disease who have catheters in place for only several hours (13).
2. Insertion of intravenous catheter: The insertion of an intravenous catheter for the infusion of fentanyl will be performed using local anesthesia and aseptic technique. The risks of an IV-line may include pain at the insertion site and superficial infection as well as local bruising. These risks are reduced by using local anesthesia and aseptic techniques.

3. Fentanyl infusion: Fentanyl has been used in clinical anesthesiology as an opioid analgesic for over 50 years. Possible side effects of acute fentanyl exposure include bradycardia, nausea, respiratory depression, and rarely chest wall rigidity. Before the start of the fentanyl infusion protocol subjects will be given Ondansetron to minimize the risk of nausea. Atropine or Robinol may be given to prevent/treat bradycardia. Chest wall rigidity is a rare occurrence at the fentanyl concentrations and slow infusion we are proposing, but can be reversed quickly with either naloxone or a short-acting neuromuscular blocking agent.

The aim of the present protocol is to induce mild to moderate respiratory depression up to the described endpoint of two consecutive PaCO₂ measurements ≥ 60 mmHg. The fentanyl infusion will be stopped if: (1) the partial pressure of carbon dioxide exceeds 60 mm Hg in two consecutive blood gas measurements (primary end-point), (2) the subject requires positive pressure bag/mask assisted ventilation by the anesthesiologist, or (3) the hemoglobin oxygen saturation falls below 90% on supplemental oxygen (FIO₂ = 1.0), (4) one blood gas of PaCO₂ > 70 mmHg, and/or (5) two consecutive blood gas measurements with pH < 7.20 .

Potential Benefits of Proposed Research to Human Subjects & Others- Risk/Benefit Ratio:

The risks of a slow intravenous infusion of fentanyl to induce hypoventilation managed by an experienced anesthesiologist are low. We do not anticipate any benefits of participating in this study to the human volunteer subjects. The benefit of developing an algorithm capable of detecting and preventing severe hypoventilation, hypoxemia and death due to an opioid overdose is significant. The clinical investigative team has a variety of systems and procedures in place to maximize subject safety. In the United States opioid related overdose is currently a leading cause of death in people aged <50 years (1). An accurate tool to alert first responders or family and friends in the case of an impending overdose would have significant societal impact and would potentially prevent a significant number of deaths by allowing for the timely administration of naloxone. In the hospital setting there is also a need for a continuous monitor of minute ventilation (MV = RR x TV) to improve the safety of opioid analgesia (5).

H. Data and Safety Monitoring Plan

Medical Monitor: [name] will serve as medical monitor. A medical monitor is a physician that is independent of the research team. [name] has extensive educational and professional experience to serve as a subject advocate. He will monitor subject enrollment and will discuss research progress with the Principal Investigator. He is also required to review all unanticipated problems involving risk to subjects or others, serious adverse events and any subject deaths associated with the protocol and provide an unbiased written report of the event. At a minimum, the medical monitor must comment on the outcomes of the event or problem and in case of a serious adverse event or death, comment on the relationship to participation in the study. The medical monitor must also indicate whether he/she concurs with the details of the report provided by the Principal Investigator. Reports for events determined by either the investigator or medical monitor to be possibly or definitely related to participation and reports of events resulting in death must be promptly forwarded to the Western IRB.

The medical monitor will also monitor any protocol deviations and/or protocol violations. He will promptly report any discrepancies or problems to the IRB. The medical monitor also has the authority

to stop the research in progress, remove individual subjects from the research, and take whatever steps are necessary to protect the safety and well-being of the subjects until the IRB can assess the monitor's report.

The Principal Investigator, [name], will be responsible for accuracy and confidentiality of written and electronic participant data. Accuracy of the data will be confirmed by [name] and the monitor before the study data set is locked and before the research is published in a peer reviewed journal.

I. Literature Cited

1. <http://wonder.cdc.gov/mcd.html>. Multiple cause of death data 2018 [

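### No written rule holds a timed fentanyl step after a single PaCO₂ of 60 to 70 mm Hg, and the PaCO₂ stop (above 60) does not match the endpoint (60 or above)

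*Protocol*

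**What the plan says.** **Dosing.** Protocol section D (Visit # 2) gives a 1.0 mcg/kg bolus and then a stepped infusion: "The infusion will start at 1.5 mcg/kg/hr and will be increased by 1.5 mcg/kg every 30 minutes". It adds: "The infusion will be continued for a maximum duration of 3 hours (final infusion rate 9.0 mcg/kg/h". No PaCO₂ condition is attached to a step.

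**Sampling.** Section D: "Arterial blood gases will be measured every 10 minutes, or immediately after the decision is made to stop the infusion protocol".

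**Stops.** Section D stops the infusion early if "the PaCO₂ exceeds 60 mm Hg in two consecutive blood gas measurements (primary end-point", if assisted ventilation is needed, or if SaO₂ falls below 90% on oxygen. Section G (Specific Procedures and Risks) repeats these, with the PaCO₂ stop as "the partial pressure of carbon dioxide exceeds 60 mm Hg in two consecutive blood gas measurements (primary end-point", and adds two more: "one blood gas of PaCO₂ > 70 mmHg, and/or (5) two consecutive blood gas measurements with pH < 7.20". Section D does not list those two.

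**Endpoint.** Section D describes moderate hypoventilation as "defined as two consecutive arterial PaCO₂ measurement ≥ 60 mmHg". Section G uses the same threshold of 60 or above when it states the aim.

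**Use of the ramp.** Section E evaluates the algorithm partly by "comparing predicted time to hypoventilation during the fentanyl ramp vs. the observed time to hypoventilation".

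**The concern.** The rules say when to stop but not when to wait. After one PaCO₂ of 60 to 70, the decision rests on a gas about 10 minutes later, and nothing in the text suspends a rate increase that falls due in between. Of the five stops in section G, the pH stop also needs two gases, and the single-value stop above 70 can act only once a further gas is drawn. Inside the interval itself, the written triggers left are low saturation and assisted ventilation. Supplemental oxygen is given precisely to prevent low saturation.

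What is at stake is a little more opioid than needed, given to a healthy volunteer who is expected to gain no benefit (section G), at a moment when the latest gas is already at the target.

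A separate inconsistency sits in the same rule. The stop carries the label of primary endpoint but uses a strict inequality, while the endpoint includes 60 itself. A pair such as 60 and 65 reaches the endpoint and, by that rule, leaves the infusion running.

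**Working it through.** **Inputs (Protocol section D).** Bolus 1.0 mcg/kg; starting rate 1.5 mcg/kg/h; increment 1.5 every 30 minutes; maximum 3 h; gases every 10 minutes. The increment is printed without a per-hour unit, so I check that reading first.

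**Reproducing the plan's figure.** Six half-hour rates: 1.5, 3.0, 4.5, 6.0, 7.5, 9.0 mcg/kg/h. The last equals the stated final rate, so the increment is per hour. Full ramp = 1.0 + 0.5 × (1.5 + 3.0 + 4.5 + 6.0 + 7.5 + 9.0) = 1.0 + 15.75 = 16.75 mcg/kg.

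**How many waiting intervals contain a step.** Assume gases at 10, 20, …, 180 minutes on the same clock as the steps. A first high value that can be confirmed within the ramp falls at 10 to 170 minutes, giving 17 intervals. Steps fall at 30, 60, 90, 120 and 150 minutes, so the intervals 30–40, 60–70, 90–100, 120–130 and 150–160 contain one: 5/17 = 29%. Shifting the gas clock by 1, 5 or 9 minutes still gives 5 of 17.

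If a confirming gas is drawn at the step time and the step is made before its result is read, the count becomes 10 of 17. I leave out those further five because the extra dose there lasts only for the analyzer turnaround.

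**Extra dose per step.** 1.5 × 10/60 = 0.25 mcg/kg by the confirming gas; × 70 kg = 17.5 mcg.

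**Against cumulative dose at the confirming gas, bolus included (mcg/kg):**

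| Step (min) | Rate change | Confirming gas (min) | With step | Without step | Increase |
|---|---|---|---|---|---|
| 30 | 1.5 to 3.0 (+100%) | 40 | 2.25 | 2.00 | 12.5% |
| 60 | 3.0 to 4.5 (+50%) | 70 | 4.00 | 3.75 | 6.7% |
| 90 | 4.5 to 6.0 (+33%) | 100 | 6.50 | 6.25 | 4.0% |
| 120 | 6.0 to 7.5 (+25%) | 130 | 9.75 | 9.50 | 2.6% |
| 150 | 7.5 to 9.0 (+20%) | 160 | 13.75 | 13.50 | 1.9% |

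The last column is the increase over the dose without the step. As a share of the dose actually given, the range is 0.25/2.25 = 11.1% to 0.25/13.75 = 1.8%.

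**Threshold mismatch.** Take consecutive values 60 and 65. Endpoint (≥ 60 twice): met. PaCO₂ stop (> 60 twice): not met, because the first value does not exceed 60. Unless another stop applies, the infusion runs at least until the next gas.

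**The case against.** The strongest reply is that this is an inference from silence. The protocol does not expressly order a step after a high gas. A board-certified anesthesiologist manages every subject and may hold a step on judgement, with continuous CO₂ waveform, airflow and pulse oximetry in view, BIS monitored and naloxone at hand. Figure 2, titled as the infusion protocol, is not shown and might contain a hold. Reaching PaCO₂ of 60 twice is the purpose of the study, so a first value of 60 to 70 is expected on the way. The extra 0.25 mcg/kg is a quarter of the opening bolus and lies inside the planned ramp. A hold triggered by PaCO₂ also makes the ramp depend on the outcome before the endpoint, which touches the comparison in section E.

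Most of this stands, and it limits the size of the point. It does not supply a hold rule: clinical oversight is general, and the written default for the rate is the clock. As for the ramp, it already ends on PaCO₂, so it is not independent of the outcome today.

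Three stronger readings are tempting, and the text does not support them:

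- **That the schedule contradicts the aim.** It does not. The endpoint is the confirmed pair, and continuing after one high value is consistent with seeking it.
- **That 29% of subjects would be exposed.** The 5 of 17 counts clock slots. The protocol does not say when first high values occur.
- **That exposure rises by 20% to 100%.** Those are rate changes. Cumulative dose rises by 12.5% at most, and that case needs a PaCO₂ of 60 at 30 minutes, after only the bolus and the lowest rate.

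**Conclusion.** The point holds as a modest safety refinement plus a separate wording error. On the text alone, steps are purely time-driven and nothing holds one after a single PaCO₂ of 60 to 70. The consequence is 0.25 mcg/kg per affected interval. No effect on PaCO₂ can be estimated from the document, and no harm is shown. The count of 5 of 17 assumes 10-minute gases kept to schedule through the full 3 hours. The upper limit of 70 comes from section G; section D on its own gives none.

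The threshold mismatch does not depend on the hold argument and is plain on the page. It matters only when a value is exactly 60. How often that occurs is unknown, since the protocol does not give the analyzer's reporting resolution.

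Both are worth considering. Neither affects sample size or an error rate.

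**What to change.** 1. In sections D and G, write stop (1) as: *PaCO₂ ≥ 60 mm Hg on two consecutive gases*. This matches the endpoint.
2. In section D, after the infusion schedule, add: *No rate increase is made while the latest PaCO₂ is ≥ 60 mm Hg. At a shared time point the gas is read before the step. A held step is given if the next gas is < 60, and later steps keep their clock times.*
3. Record the actual infusion rates and times for each subject.

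The first change makes the second workable. With both at ≥ 60, the next gas either stops the infusion or releases the step, so a hold lasts one interval. With the present strict inequality, repeated values of exactly 60 would hold the step without ending the infusion.

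**Costs.**

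- Each hold forgoes 0.25/16.75 = 1.5% of the full ramp. The most possible is five holds: 1.25/16.75 = 7.5%.
- Steps wait for the analyzer in every subject. Turnaround is not given; at an assumed 1 to 5 minutes for all five steps, the loss is 5 × 1.5 × t/60 = 0.125 to 0.625 mcg/kg, or 0.7% to 3.7%.
- The ramp will differ slightly between subjects in the time-to-hypoventilation comparison of section E, which is why the actual rates should be recorded.
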